6. METHODS OF MINIMISING BIAS

6.1. Randomization

We will use a computerized randomization list (www.randomization.com) using block randomization of 10 to assure proper distribution during each group of students.

6.2. Blinding

There will be no blinding in this study because the participants will realize the difference in the teaching method.

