4.2 Outcomes

Our primary outcome will be the percentage of correct compressions obtained from the printed report from the LSR. With this parameter we will compare the two groups directly after the first teaching session.

Our secondary outcomes are:

- The subcomponents of the printed report from the LSR (ventilation volume, number of ventilations per minute, overall ventilation volume, number of ventilations, percentage of correct ventilations, number of ventilations with too much volume, number of ventilations with too little volume, number of ventilations that were too fast, the relation between ventilations and compressions, compression depth, number of compressions per minute, compression frequency, total number of compressions, percentage of correct compressions, number of compressions that were too deep, number of compressions that were too shallow, incorrect hand position, and incorrect decompression).
- The score on the BLS/AED provider assessment record(13) (fig.2).
- Degree of loss of competence after four months for all the primary and secondary outcomes.
- Influences of gender and prior BLS training will also be investigated, as well as the decay of competences.

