5.2. Procedures

When participants attend the “Erweiterte Erste Hilfe für Studierende der Humanmedizin” they will receive a short introduction about the study. We will invite all first year students to participate in the study. As the study is voluntarily, participants will need to sign a written informed consent. After that we will randomize the students to either group A or Group B (see figure 1). Group A will train their technical CPR-skills with supervision by a tutor (either general practitioner or medical student, all trained in CPR teaching) and group B will train without supervision. The participants in group B will not be allowed to communicate with each other during the training. The training will take about 40 minutes for each group. Directly after the training each group will be tested and the printed report form from the LSR will be obtained for each participant. In the test the students will perform CPR in a simulated scenario as a first responder. The scenario is: “A male person has collapsed in the hall of the university and you cross by. No other persons are present at the moment.” The participant should start CPR as learned in the training. During the CPR a departmental research fellow will observe the study participants and record BLS/AED actions on a scoring sheet.

To avoid struggle with the equipment, each student will be given two minutes to familiarize themselves with the testing manikin and the equipment (an AED). We will record three cycles of two minutes CPR (with five times 30:2 compression : ventilation intervals, as recommended by the current international resuscitation guidelines) (14). During the three cycles an AED will be delivered and the study participant has to apply the AED and deliver a shock – after that the study terminates. After the BLS/AED competence testing, both groups will continue the rest of their first aid course together and the first part of the study ends. Four months later we will repeated the same scenario over the same time interval and record the same parameters. At the end of the second testing, a short feedback will be provided on the BLS/AED competence and further practice will be provided to the students to improve their CPR competence. From this point forward no further data will be collected

[figure not shown]

Figure 1: Procedure

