8.2. Assessment of secondary outcomes

The secondary outcomes are:

- The subcomponents of the printed report from the LSR.
- The score on the BLS/AED provider assessment record.
- Degree of loss of competence after four months for all the primary and secondary parameters.

The printed report from the LSR consists of ventilation volume, number of ventilations per minute, overall ventilation volume, number of ventilations, percentage of correct ventilations, number of ventilations with too much volume, number of ventilations with too little volume, number of ventilations that were too fast, the relation between ventilations and compressions, compression depth, number of compressions per minute, compression frequency, total number of compressions, percentage of correct compressions, number of compressions that were too deep, number of compressions that were too shallow, incorrect hand position, and incorrect decompression. We will record these parameters over the entire testing period. We will look at each parameter individually.

To assess the score on the BLS/AED provider assessment record(13) (fig. 2) during the simulated scenario a departmental research fellow will observe the study participants and record BLS/AED actions on a scoring sheet. Actions recorded are: Check response, assess breathing, call emergency services, chest compressions, rescue breaths, compression : ventilation ratio, activate AED, attach

pads, stand clear, deliver shock, follow AED instructions, and CPR. Time to first chest compression and time to first shock will also be measured.

		BLS/AED PROVIDER ASSESSMENT RECORD		2016.v.1.
Candidate Name:		Date:	Instructor:	
Skill	The candidate	Achieved		Comments
		Yes	No	
Check response	Demonstrates gently shaking and shouting to establish responsiveness			
Assess breathing	Demonstrates head tilt and chin lift			
Assess breathing	Demonstrates look, listen and feel for normal breathing for no more than 10 sec (does not count aloud)			
Call emergency services (Get help)	Describes how to phone for emergency services: 112, unresponsive and non-breathing victim, AED			
Chest compressions	Demonstrates effective chest compressions; rate 100-120/min, depth 5-6 cm; hand position: centre of the chest. Minimises interruptions in chest compressions			
Rescue breaths	Demonstrates rescue breaths sufficient to cause the chest to rise and fall			
Compression : ventilation ratio	Demonstrates ratio of 30 compressions to 2 ventilations			

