Activate AED	Switch the AED on or, if a helper is present, ask him/her to do it			
Attach pads	Demonstrates attaching pads in correct position			
Stand clear	Allows rhythm analysis whilst making sure that nobody touches the victim (including visual sweep and verbal instruction)			
Deliver shock	Demonstrates rapid and safe delivery of a shock (including visual sweep and verbal instruction to stand clear)			
Follow AED instructions	Demonstrates listening to and executing AED instructions			
CPR	Minimises interruptions in chest compressions and demonstrates correct sequence in ratio of 30 compressions to 2 ventilations			

Successful completion: Yes No

Figure 2: Procedure

By doing the same test four months later, we can measure the loss of competence by comparing the percentage of correct compressions and the subcomponents of the printed report, and compare the score on the BLS/AED provider assessment record.

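### Section 6.2 rules out all blinding for a reason that covers participants only, leaving unmasked the research fellow who scores the partly judgement-based BLS/AED record, a listed secondary outcome

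*Combined protocol and SAP*

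**What the plan says.** Section 6.2 is one sentence: "There will be no blinding in this study because the participants will realize the difference in the teaching method". It stands under the chapter on minimising bias, and no other section adds to it.

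Section 5.2 describes how the record is scored: "During the CPR a departmental research fellow will observe the study participants and record BLS/AED actions on a scoring sheet". The same section describes the group A tutors separately, as general practitioners or medical students trained in CPR teaching. On timing it says "Directly after the training each group will be tested". The two groups then finish the course together, and the same scenario is repeated four months later.

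The score on the record is a listed secondary outcome in 4.2 and appears in the objective in 4.1. Section 4.2 also lists "Degree of loss of competence after four months for all the primary and secondary outcomes", and 8.2 plans to "compare the score on the BLS/AED provider assessment record" between the two tests. Under 8.3 the fellow also rates each student's competence from 0 to 100. That rating is among the other study variables and is not a listed outcome.

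The primary outcome (4.2, 8.1) is the percentage of correct compressions from the manikin's printed report.

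**The concern.** The reason given in 6.2 concerns what students will notice about their own training. It does not bear on whether the person scoring them must know which training they had. Blinding participants and masking the assessor are separate decisions, and the plan gives a reason only for the first.

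This matters because the fellow's scores are an outcome. If the fellow knows the arm and expects one method to do better, the judged parts of the form can create or hide a difference between arms, at either test. No section masks the fellow, keeps the fellow away from training or the randomisation list, or provides a second rater.

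**Working it through.** **1. How much of the form is judged.** Figure 2 in 8.2 has 7 rows up to the compression:ventilation ratio and 6 AED and CPR rows after it: 7 + 6 = 13, each scored Yes or No. (The text of 8.2 names 12 actions because it lists breathing assessment once.) Three rows contain terms without a threshold:

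| Row | Judged part | Anchored part |
|---|---|---|
| Chest compressions | "Demonstrates effective chest compressions"; also minimising interruptions | rate, depth, hand position |
| Deliver shock | "Demonstrates rapid and safe delivery of a shock" | visual sweep, verbal instruction |
| CPR | "Minimises interruptions in chest compressions and demonstrates correct sequence": the interruptions part | 30:2 ratio and sequence |

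That is 3/13 = 23% of the rows, each only partly judged. Rescue breaths, where chest rise is judged by eye, could be counted as a fourth (4/13 = 31%), so three is a cautious count.

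**2. Arm sizes.** Section 9.1 gives 150 subjects for 64% versus 84%, α 0.05, power 80%. With a two-sided test, pooled variance and no continuity correction:

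n per arm = [1.960·√(2·0.74·0.26) + 0.842·√(0.64·0.36 + 0.84·0.16)]² / 0.20² = 74.3, rounded up to 75, so 150 in total.

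The plan's figure reproduces. With equal allocation the arms are 75 (of 150) or 100 (of the 200 to be recruited).

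**3. Illustration of size.** None of the following inputs is in the documents: the score is an unweighted sum of 13 items; its SD is 1.5, 2 or 2.5; there is no true difference; the fellow passes one arm more often, by b, on three rows. The t-test is one of the two tests allowed in 9.2.

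Shift d = 3b. Standard error = SD·√(2/n). The rejection rate is that of a two-sided 5% t-test with noncentrality d/SE.

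Example: b = 0.05 gives d = 0.15 points (0.15/13 = 1.2% of the scale). With SD 1.5 and n = 75, SE = 1.5·√(2/75) = 0.245, noncentrality = 0.15/0.245 = 0.61, rejection rate = 9.3%.

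| Leniency b | Shift | 75 per arm, SD 1.5 / 2 / 2.5 | 100 per arm, SD 1.5 / 2 / 2.5 |
|---|---|---|---|
| 0 | 0 | 5% | 5% |
| 5 points | 0.15 | 9.3% / 7.4% / 6.5% | 10.8% / 8.2% / 7.1% |
| 10 points | 0.30 | 23% / 15% / 11% | 29% / 18% / 13% |

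As a check with the Mann-Whitney test, which 9.2 also allows, simulated 13-item scores (6000 runs, SD about 1.7 to 2.4, 5 points of leniency) gave 6.6% to 8.7% at 75 per arm and 6.9% to 9.6% at 100.

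**4. Four-month loss.** Let S1 and S2 be a student's unbiased scores and L the same leniency at both tests. Absolute loss is (S1 + L) − (S2 + L) = S1 − S2, so L cancels. Relative loss is (S1 − S2)/(S1 + L), so it does not. The plan does not define degree of loss, so which case applies is open. If only the second test is masked, the whole first-test shift, 0.15 points in the 5-point example, enters the absolute-loss contrast.

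**The case against.** The strongest reply is that the reach is narrow. The primary outcome and most of the secondary outcomes come from the manikin report. What remains is part of one secondary score and a rating that is not a listed outcome, and the plan states openly that nobody is blinded. This stands, and it limits the weight of the point. It does not supply the missing reason: the score is named in the objective, and the fellow is described separately from the tutors.

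A second reply is practical. Each group is tested directly after its own training, so test order may reveal the arm and students may disclose it. This also stands for the first test. It has less force at four months, when no group-specific training comes immediately before the test.

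A third reply is that the numbers are assumed. That is correct. The result is driven mainly by the leniency value, for which there is no source, and the score is undefined. The only overall result printed on the form is a yes/no for successful completion; if that is the score, the table in the working does not apply.

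A reader might also infer that three rows are wholly subjective. They are not: each has anchored elements, and only the unanchored part is exposed.

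**Conclusion.** The point holds as a cheap improvement. Section 6.2 gives a reason for not blinding participants and applies it to everyone, so a listed secondary outcome is scored by an observer with no protection against knowing the arm.

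The documents give no size for the resulting bias. Under the stated assumptions the false-positive rate on the record score runs from 5% with no leniency, through about 6.5% to 11% with 5 points, to about 11% to 29% with 10 points. The case rests on the missing safeguard, not on these figures.

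Three stronger readings are tempting, and the documents do not support them:

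- That the main result is compromised by observer scoring. It is not, because the manikin records it.
- That the fellow will know the arm and score unfairly. The documents do not say what the fellow will know; they only provide no safeguard.
- That the four-month loss is necessarily biased, or necessarily free of bias. Equal leniency at both tests cancels only if loss is an absolute within-student difference, which is not defined.

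**What to change.** Replace 6.2 with:

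> Participants and tutors are not blinded. Where feasible at each test, the research fellow who scores the BLS/AED record and the 0-100 rating is not told the allocation and takes no part in training or in handling the randomisation list; students are identified by study code and asked not to reveal their group. Where a test cannot be masked, the reason is stated and the observer-scored results are reported as unmasked.

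If only the four-month test can be masked, still report the between-arm comparison of loss, with the caveat that the first scores were unmasked. Dropping that comparison would remove a listed secondary outcome and is not needed.

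The cost is protocol wording and test-day logistics. Sample size and significance level do not change. The wording asks for masking where feasible, so it does not require a replacement scorer; the documents do not say whether the fellow has a role in training or randomisation. The downside is imperfect masking, especially at the first test, because each group is tested straight after its training.

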7. PROJECT POPULATION

7.1. Participants

All first year medical students at the University of Bern participating in the course “Erweiterte Erste Hilfe für Studierende der Humanmedizin”.

7.2. Inclusion criteria

First year medical students at the University of Bern participating in the course “Erweiterte Erste Hilfe für Studierende der Humanmedizin” with written informed consent.

7.3. Exclusion criteria

Students with professional BLS-experience, unable to perform BLS, or missing informed consent will be excluded.

7.4. Criteria for withdrawal

The participants can withdraw their consent and leave the study at any time.

8. PROJECT ASSESSMENT

8.1. Assessment of primary outcome

Our primary outcome will be the percentage of correct compressions obtained from the printed report from the LSR.

8.2. Assessment of secondary outcomes

The secondary outcomes are:

- The subcomponents of the printed report from the LSR.
- The score on the BLS/AED provider assessment record.
- Degree of loss of competence after four months for all the primary and secondary parameters.

The printed report from the LSR consists of ventilation volume, number of ventilations per minute, overall ventilation volume, number of ventilations, percentage of correct ventilations, number of ventilations with too much volume, number of ventilations with too little volume, number of ventilations that were too fast, the relation between ventilations and compressions, compression depth, number of compressions per minute, compression frequency, total number of compressions, percentage of correct compressions, number of compressions that were too deep, number of compressions that were too shallow, incorrect hand position, and incorrect decompression. We will record these parameters over the entire testing period. We will look at each parameter individually.

To assess the score on the BLS/AED provider assessment record(13) (fig. 2) during the simulated scenario a departmental research fellow will observe the study participants and record BLS/AED actions on a scoring sheet. Actions recorded are: Check response, assess breathing, call emergency services, chest compressions, rescue breaths, compression : ventilation ratio, activate AED, attach

pads, stand clear, deliver shock, follow AED instructions, and CPR. Time to first chest compression and time to first shock will also be measured.

		BLS/AED PROVIDER ASSESSMENT RECORD		2016.v.1.
Candidate Name:		Date:	Instructor:	
Skill	The candidate	Achieved		Comments
		Yes	No	
Check response	Demonstrates gently shaking and shouting to establish responsiveness			
Assess breathing	Demonstrates head tilt and chin lift			
Assess breathing	Demonstrates look, listen and feel for normal breathing for no more than 10 sec (does not count aloud)			
Call emergency services (Get help)	Describes how to phone for emergency services: 112, unresponsive and non-breathing victim, AED			
Chest compressions	Demonstrates effective chest compressions; rate 100-120/min, depth 5-6 cm; hand position: centre of the chest. Minimises interruptions in chest compressions			
Rescue breaths	Demonstrates rescue breaths sufficient to cause the chest to rise and fall			
Compression : ventilation ratio	Demonstrates ratio of 30 compressions to 2 ventilations			
Activate AED	Switch the AED on or, if a helper is present, ask him/her to do it			
Attach pads	Demonstrates attaching pads in correct position			
Stand clear	Allows rhythm analysis whilst making sure that nobody touches the victim (including visual sweep and verbal instruction)			
Deliver shock	Demonstrates rapid and safe delivery of a shock (including visual sweep and verbal instruction to stand clear)			
Follow AED instructions	Demonstrates listening to and executing AED instructions			
CPR	Minimises interruptions in chest compressions and demonstrates correct sequence in ratio of 30 compressions to 2 ventilations			

Successful completion: Yes No

Figure 2: Procedure

By doing the same test four months later, we can measure the loss of competence by comparing the percentage of correct compressions and the subcomponents of the printed report, and compare the score on the BLS/AED provider assessment record.

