9. STATISTICAL METHODOLOGY

9.1. Determination of Sample Size

Based on a pilot study with 14 participants we calculated a median of 84% correct compressions. The interquartile range was 47% to 93%. We have discussed in the study group that a 20% decrease in percentage of correct compressions would have a clinically impact. Therefore, using a two-sample proportion test with a significance level α of 0.05 and an effect size of 20% (from 64% to 84%) we calculate that it requires 150 subjects to reach a power of 80%. To compensate for drop-outs, we aim to include 200 participants in the study.

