9.2. Planned analysis

All data will be summarized for each individual and a summary of all study participants will be computed. Data will be presented as mean (SD) or %.

Parametric data will be compared by a Students-t test, non-parametric by Mann-Whitney-U test. A $p < 0.05$ is considered as statistically significant.

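### Compression rate is right only inside 100-120/min, but it and its four-month loss are compared as raw values with no target and no direction

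*Combined protocol and SAP*

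**What the plan says.** Sections 4.2 and 8.2 make compression depth, compressions per minute, compression frequency and ventilation volume separate secondary outcomes taken from the manikin's printed report. On how they are handled, section 8.2 says: "We will record these parameters over the entire testing period. We will look at each parameter individually".

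The target appears only in the observer's checklist (Figure 2, in section 8.2): "Demonstrates effective chest compressions; rate 100-120/min, depth 5-6 cm; hand position: centre of the chest". That line is a single yes/no item, and it also asks for few interruptions.

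Section 9.2 summarises data as mean (SD) or % and names two tests: "Parametric data will be compared by a Students-t test, non-parametric by Mann-Whitney-U test".

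Section 4.2 extends loss to every outcome: "Degree of loss of competence after four months for all the primary and secondary outcomes". The end of section 8.2 says how: "we can measure the loss of competence by comparing the percentage of correct compressions and the subcomponents of the printed report". Nowhere is a target range, an in-range indicator, a distance from target or a direction of loss given for the manikin values.

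**The concern.** Most items on the report have a natural direction: more correct compressions is better, and more faults is worse. Compression rate has none. It is good in the middle and bad at both ends. A test of location answers whether one arm compresses faster than the other, not whether one arm compresses at the right rate more often.

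Three things follow.

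- Students who are too slow and students who are too fast offset each other, so two arms with very different adherence can have the same mean.
- Two arms in which almost everyone is in range can differ significantly.
- A change in rate over four months has no meaning as competence unless one knows where the student started relative to the window.

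Section 2 asks whether the two methods give the same skills, so a finding of no difference would itself be reported as a result. On rate, equal means would not support it.

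**Working it through.** **Inputs.** The window of 100-120/min is from Figure 2. The tests are from section 9.2. The arm sizes are 75 (150 in total) and 100 (200 in total), from section 9.1 with equal allocation. The documents give no mean or SD for rate, so those used below are assumptions, varied over a range.

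**1. The plan's own figure.** For 64% versus 84%, two-sided α 0.05, power 80%, pooled variance (average proportion 0.74) and no continuity correction:

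n = [1.96·√(2·0.74·0.26) + 0.842·√(0.64·0.36 + 0.84·0.16)]² / 0.20² = [1.216 + 0.508]² / 0.04 ≈ 74.3, rounded up to 75 per arm, or 150 in total.

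The stated 150 is reproduced. It concerns the primary outcome, and nothing below changes it.

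**2. Equal means, unequal adherence.** For a normal rate with mean 110 and SD s, the share in range is 2Φ(10/s) − 1. This gives 79% for SD 8, 68% for SD 10, 60% for SD 12, 50% for SD 15 and 38% for SD 20. The rejection rates below are simulated: 1,500 trials per row, and 4,000 for the last row. The in-range test is Fisher's, except chi-square in the last row.

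| SDs | In range | n per arm | t-test, raw | Mann-Whitney, raw | In-range yes/no | Mann-Whitney, distance outside |
|---|---|---|---|---|---|---|
| 10 v 12 | 68% v 60% | 75 | 5% | 5% | 15% | 25% |
| 10 v 15 | 68% v 50% | 75 | 4% | 5% | 62% | 82% |
| 10 v 20 | 68% v 38% | 75 | 6% | 6% | 96% | 99.8% |
| 10 v 12 | 68% v 60% | 100 | 5% | 5% | 20% | 32% |
| 10 v 15 | 68% v 50% | 100 | 5% | 5% | 73% | 91% |
| 10 v 20 | 68% v 38% | 100 | 5% | 5% | 99% | 100% |
| 8 v 20 | 79% v 38% | 100 | 5.5% | 6.7% | >99% | not run |

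The planned tests reject at about α in every row. In the extreme case, half of one arm centres on 90/min and half on 130/min, against an arm centred on 110/min (all SDs 5, 75 per arm). The mean difference is about 0. The t-test rejects in 5% of trials and Mann-Whitney in 10%; both target-based comparisons reject in 100%.

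**3. The reverse case.** Take means of 107 and 112/min, SD 4, 100 per arm. The shares in range are Φ(3.25) − Φ(−1.75) = 96% and Φ(2) − Φ(−3) = 98%. The standardised difference in means is 5 / (4·√(2/100)) = 8.8, so the t-test is significant in essentially every trial although nearly all students are correct.

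**4. Four-month change.** Distance outside the window is max(0, 100 − rate, rate − 120).

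| First to second test | Raw change | Distance outside | What happened |
|---|---|---|---|
| 90 to 105/min | +15 | 10 to 0 | improved |
| 110 to 125/min | +15 | 0 to 5 | worsened |
| 130 to 115/min | −15 | 10 to 0 | improved |

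The same raw change of +15 is an improvement in one student and a deterioration in another. No sign convention for the raw change can repair this.

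**5. What the plan already has for each parameter.**

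- Depth: counts of too deep and too shallow compressions, and the percentage of correct compressions.
- Ventilation volume: counts of too much and too little, and the percentage of correct ventilations.
- Compression rate: no too-fast or too-slow count among the report items. The one stated in-range judgement is the bundled checklist item.

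**The case against.** Four stronger readings are tempting, and the documents do not support them.

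- A reader might infer that nothing in the plan separates a correct from an incorrect rate. The Figure 2 item does judge rate, its score is a secondary outcome, and it is repeated at four months. What stands is that one observer-rated yes/no answer covers rate, depth, hand position and interruptions together, in a study that section 6.2 says is not blinded. It cannot isolate rate.
- A reader might infer that the plan would count improvement as loss. Section 8.2 speaks only of comparing the two tests and gives no subtraction or sign. The supportable statement is that direction is unspecified and that no direction on the raw scale would work.
- A reader might infer that depth and ventilation volume are equally exposed. As raw values they are, but the fault counts and percentages correct have a clear direction and carry most of the information.
- A reader might infer that the main result is at risk. The percentage of correct compressions has a clear direction, and the sample size rests on it alone.

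The size of the effect is also open to challenge. The SDs are assumed, and 8 versus 20 is a strong case. With 10 versus 12, the better measure has only 25-32% power. Cancellation needs faults on both sides of the window; if they lie mostly on one side, the planned tests can show them. Section 9.2 reports SDs, so a large difference in spread would be visible even where the p-value misses it, and its allowance for % does not rule out an in-range summary. All of this limits the weight of the point. None of it supplies a target-based comparison of rate or a usable definition of its loss.

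**Conclusion.** The point holds for compression rate and, more weakly, for depth and ventilation volume as raw values. It is a worthwhile improvement to secondary outcomes, not a threat to the trial's main comparison.

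How much cancellation costs depends on assumed distributions centred in the window. Over the range examined with 75 per arm, the planned tests stay at about 5%, while Mann-Whitney on distance outside the window rejects in 25% to 99.8% of trials. If the faults in practice lie on one side, the gain is smaller. The four-month part rests on no such assumption: whatever the distribution, a raw change in rate is neither gain nor loss until it is set against the window.

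**What to change.** In sections 8.2 and 9.2:

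- **Compression rate.** Compare the arms on each student's distance outside 100-120/min (0 if inside) by Mann-Whitney as the lead measure, with the proportion of students in range as support. Define four-month loss as an increase in that distance.
- **Which report item.** State to which item the window applies, since compressions per minute and compression frequency are listed separately and not defined. Section 5.2 describes five 30:2 intervals in a two-minute cycle, which is 5 × 30 / 2 = 75 compressions delivered per minute. If the per-minute item includes the pauses for ventilation, the window cannot be applied to it.
- **Depth and ventilation volume.** Base the comparison and the loss on the existing fault counts, as a share of compressions or ventilations, and on the percentages correct. This needs no numeric limit for volume, which the documents do not give.
- **Raw rate, depth and volume.** Report as description only.

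The cost is wording and one or two derived variables from values already on the printed report. The in/out split loses some information, which is why distance should lead. A limit remains: a student who alternates between 90 and 130/min averages 110/min and still counts as inside, so a student-level mean rate can hide variation within a student.

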3. HYPOTHESIS

Our 0-hypothesis is that the students in the self-learning group will demonstrate the same BLS skills as students in the instructor-led group. The alternative hypothesis is that there will be a difference in the BLS skills demonstrated by the self-learning group compared to the instructor-led group.

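### About 18 to 20 secondary outcomes at two time points share one unadjusted p < 0.05 rule, so about two chance 'significant' differences are expected if the methods are equal

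*Combined protocol and SAP*

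**What the plan says.** Section 4.2 fixes a single primary outcome, "Our primary outcome will be the percentage of correct compressions obtained from the printed report from the LSR", and a single time for it: "With this parameter we will compare the two groups directly after the first teaching session".

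Sections 4.2 and 8.2 then list as secondary outcomes the components of the manikin report, the score on the BLS/AED assessment record, and the loss of competence at four months for all of these. Of the manikin parameters, section 8.2 says: "We will look at each parameter individually". The same section adds time to first compression and time to first shock as measurements. Section 5.2 repeats the test, with the same parameters, four months later.

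Section 9.2 has one analysis rule: "Parametric data will be compared by a Students-t test, non-parametric by Mann-Whitney-U test". A p value below 0.05 "is considered as statistically significant". It does not separate primary from secondary outcomes. The documents give no multiplicity correction, no order of testing, and no statement that secondary results are exploratory.

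The alternative hypothesis in section 3 is that "there will be a difference in the BLS skills demonstrated by the self-learning group compared to the instructor-led group". It names neither an outcome nor a time.

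**The concern.** Read together, sections 3, 8.2 and 9.2 allow any one of many tests to be reported as a statistically significant difference in BLS skills. Section 3 does not say which result answers the question, and section 9.2 gives every result the same label.

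What is at stake is how the trial is read. Section 11 presents equal skills as a foundation for more training without an instructor. If the methods are in fact equal, one or two chance findings on, say, ventilation volume or hand position could be reported as a real advantage or a real deficit of self-learning, and would blur the answer from the primary comparison.

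**Working it through.** **The plan's own figure.** The documents state no number of secondary tests and no error rate for them. The only related figure is the sample size in section 9.1: 64% versus 84%, α = 0.05, 80% power, 150 subjects. Assuming a two-sided test, 1:1 allocation and pooled variance without continuity correction:

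- mean proportion = (0.64 + 0.84)/2 = 0.74
- n per arm = [1.96 × √(2 × 0.74 × 0.26) + 0.8416 × √(0.64 × 0.36 + 0.84 × 0.16)]² / 0.20² = 74.3, rounded up to 75, so 150 in total.

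The figure reproduces. It rests on one test at 0.05, so the trial is sized for the primary comparison alone.

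**Counting the further outcomes** (sections 4.2 and 8.2):

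- Manikin report: 18 parameters are listed. One is the primary, leaving 17.
- Assessment record: 1 score.
- Defined secondaries per time point: 17 + 1 = 18.
- With the two time measures, which section 8.2 says are measured but section 4.2 does not list as outcomes: 20.
- Two time points: 36 to 40 tests.

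**Expected false positives if the methods are equal.** The expected number is m × 0.05. This needs each test to have a true 5% level, but it does not depend on how the outcomes are correlated.

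- One time point: 18 × 0.05 = 0.9; 20 × 0.05 = 1.0.
- Two time points: 36 × 0.05 = 1.8; 40 × 0.05 = 2.0.

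**Adding the four-month primary parameter and the loss of competence.** The last paragraph of section 8.2 applies loss to the primary parameter, the other report parameters and the score: 1 + 17 + 1 = 19. If loss is compared between groups, the set is 36 + 1 + 19 = 56 tests, and 56 × 0.05 = 2.8. With the two times at each visit it is 40 + 1 + 19 = 60 tests, and 60 × 0.05 = 3.0. Questions about gender and prior training would add to this, but the plan does not say how many tests they involve.

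**Chance of at least one false positive.** If the tests are independent, this is 1 − 0.95^m:

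- one time point: 1 − 0.95^18 = 60%; 1 − 0.95^20 = 64%
- two time points: 1 − 0.95^36 = 84%; 1 − 0.95^40 = 87%.

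Independence is unlikely, so these are upper-end figures. A simulation with equally correlated normal test statistics gave the values below. The correlations are assumptions, because the documents give none. The 44-test row adds the two visual analogue ratings of section 8.3 at both time points.

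| Tests | Correlation 0.3 | 0.5 | 0.8 |
|---|---|---|---|
| 36 | 71% | 55% | 27% |
| 44 | 77% | 60% | 29% |

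The expected number stays at 1.8 and 2.2 throughout, apart from simulation error. Correlation makes the false positives cluster in fewer trials; it does not remove them.

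**The case against.** The strongest reply is that the plan already has the structure that matters. One primary outcome is fixed at one time, the sample size rests on it, and everything else is called secondary. Its 0.05 level is untouched by what is tested alongside it. Section 4.1 goes some way to define BLS skills as the percentage of correct compressions directly after training. Uncorrected secondary outcomes are common, and looking at a parameter is not the same as declaring it significant.

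Much of this stands. A reader might infer that the primary test is inflated or contradicted by the secondaries; the documents do not support that. But section 4.1 names the assessment score alongside the primary measure, so the tie is only partial. The usual defence of uncorrected secondaries also relies on their being labelled supportive, and section 9.2 gives them the same significance label as the primary.

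A reader might also count the 13 rows of the assessment form as separate tests and reach 17 + 13 + 1 + 2 = 33 per time point, with an 82% chance of a false positive at one visit and 97% over two. The documents do not support that count. They compare one score, the sentence about individual parameters follows the manikin list, and no test for yes/no items is named. Those percentages also assume independence, whereas compressions per minute and compression frequency, for example, plainly overlap, and the same students are tested twice.

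Finally, section 8.2 does not say whether loss of competence is compared between groups or described within them. The figures of 2.8 and 3.0 are therefore conditional.

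**Conclusion.** The point holds at a modest size. With 18 to 20 further outcomes at two time points, an unadjusted p < 0.05 rule gives 0.9 to 1.0 expected false positives per time point and 1.8 to 2.0 over both if the methods are equal. It gives about 2.8 or more if the four-month primary parameter and between-group loss comparisons are tested too. These expectations assume only that each test has a true 5% level.

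The chance of at least one false positive over both time points is 84% to 87% under independence, and lower with correlation. A reader might infer that most null trials would show a false difference. That holds in the simulation at assumed correlations of 0.3 and 0.5, but not at 0.8, so it should not be stated flatly.

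The defect lies in how secondary results may be labelled and read against a broadly worded hypothesis. It does not weaken the primary test. It is worth correcting because the correction is cheap and settles which result answers the trial's question.

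**What to change.** - In section 3, state the hypothesis test for the percentage of correct compressions directly after training.
- Name the four-month comparison as a secondary aim, so that the aim in section 2 is kept.
- In section 9.2, restrict the claim of statistical significance to that primary comparison.
- Report all other outcomes, including loss of competence, as exploratory, with between-group estimates and 95% confidence intervals and no significance label.
- If formal claims on secondaries are wanted, apply Holm or Benjamini-Hochberg within each time point, and say which. Holm is valid under any correlation. Benjamini-Hochberg controls the false discovery rate, and its standard guarantee needs independence or positive dependence. Loss-of-competence comparisons would need their own family or should stay exploratory.
- State whether checklist items will be tested singly and whether loss is compared between groups.

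The cost is wording only, with no added participants or measurements. The price is that no secondary parameter can carry a stand-alone significance claim. Under Holm, the smallest p value at a time point would have to be below 0.05/18 = 0.0028, or 0.05/20 = 0.0025 with the time measures.
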